### Study design

This study was conducted to compare the efficacy of metacarpophalangeal (MCP)-blocking orthosis with relative motion extension (RME) orthosis in patients with trigger finger between June 2021 and March 2022 at a university hospital. The study was approved by the University Institutional Research Ethics Board. Patients were informed about the study and provided written informed consent before enrolment. The inclusion criteria were patients diagnosed with Stage 1-3 trigger finger, A1 pulley triggering and aged between 18 and 60 years. We excluded patients with trigger thumb, multiple trigger fingers on one hand, neurological disorders, rheumatologic diseases, pregnancy, and patients who had received a steroid injection in the affected finger within the previous six months or who had previously undergone trigger release surgery.

Power analysis was performed using G\*Power 3.1 to test the difference between pretreatment and post-treatment means with a two-tailed test, (primary outcome was pain and function ), and an alpha of 0.05. A total sample of 30 participants was required to achieve a power of 0.90.

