# Study sample

Patients were randomly assigned in a 1:1 ratio to either the MCP-blocking group or the RME group, using a simple random sampling method. Patients were numbered according to their admission to the clinic. Randomization was performed using a random number table system. Starting with the MCP-blocking group, each group was assigned a number in turn. Patients in the MCP group received an MCP-blocking orthosis, and patients in the RME group received an RME orthosis for six weeks. All patients received patient education, activity modification, and flexor tendon gliding exercises as part of the rehabilitation program.

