### Measurements

Demographic information obtained during the pre-treatment assessment included: age, gender, affected finger, dominant hand, duration of symptoms and occupation. The primary outcome measures were performed twice, before and after treatment at six weeks. The primary outcomes were pain and function. Pain intensity was assessed using a numeric pain rating scale (NPRS). Functional status was assessed with the Disabilities of Arm, Shoulder, and Hand Questionnaire (DASH).

Satisfaction with the orthosis was a secondary outcome of this study. The Quebec Assistive Technology User Satisfaction Evaluation (Quest 2.0) was used to assess patients' satisfaction with their orthoses. Of the 12-item Quest instrument, 8 items evaluate the characteristics of the assistive device in terms of dimensions (size), weight, adjustments, safety, durability, ease of use, comfort, and effectiveness. The remaining four items evaluate service, including service delivery, repairs and service of the assistive device, professionalism of service, and follow-up service. The instrument also included an assessment of satisfaction with the device on a five-point scale. In the final section, participants were asked to select the

three most important items related to the assistive device from 12 short satisfaction statements.

Since emotional status is related to disability in trigger finger patients, the Beck Depression Scale (BDS) and the Beck Anxiety Scale (BAS) are used to determine the severity of depression and anxiety, respectively. A higher score indicates more severe depression or anxiety.

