# Statistical analysis

Descriptive analyses were presented using means and standard deviations and using medians and interquartile ranges (IQR) for the non-normally distributed and ordinal variables (using frequency tables for the ordinal variables). The normal distribution of the continuous variables was tested using visual (histogram and probability plots) and analytical methods (Shapiro-Wilk test). DASH, BDS and BAS scores was normally distributed; the NRPS and Quebec scores, age, gender, affected hand and finger, symptom duration were not normally distributed. The Student T test was used for normally distributed data and two-tailed Wilcoxon signed rank test was used for non-normally distributed data to compare pretreatment and post-treatment results. The Mann-Whitney U test was used to analyse the difference between two groups. The significance level was set at p < 0.05.

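### The 0.90 power with 30 patients is stated for a before/after change; the randomised comparison of the two orthoses, which is the trial's aim, has no power statement

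*Combined protocol and SAP*

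**What the plan says.** Under Study design, the aim is to "compare the efficacy of metacarpophalangeal (MCP)-blocking orthosis with relative motion extension (RME) orthosis in patients with trigger finger". Under Study sample, patients are "randomly assigned in a 1:1 ratio to either the MCP-blocking group or the RME group".

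The power analysis, also under Study design, is described as one "to test the difference between pretreatment and post-treatment means with a two-tailed test", with alpha 0.05 and pain and function as the primary outcomes. Its result is: "A total sample of 30 participants was required to achieve a power of 0.90". No effect size, SD, before/after correlation or dropout allowance is given.

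Under Measurements, "The primary outcome measures were performed twice, before and after treatment at six weeks". The Statistical analysis section then gives two separate sets of tests. For change over time it uses a Student t test or, in its words, "two-tailed Wilcoxon signed rank test was used for non-normally distributed data to compare pretreatment and post-treatment results". For the groups, "The Mann-Whitney U test was used to analyse the difference between two groups". No section attaches a power, target difference or sample size to that second comparison.

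**The concern.** The before/after contrast is a legitimate planned analysis, but it is not the stated aim, and randomisation is not needed for it. The Study sample section also says: "All patients received patient education, activity modification, and flexor tendon gliding exercises as part of the rehabilitation program". A change from baseline therefore mixes the effect of the orthosis with that of the shared programme and with the natural course of the condition. Both arms could improve greatly with no difference between the orthoses, or with a real difference that the trial is too small to show.

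A reader who sees a power of 0.90 will take it to cover the orthosis comparison. A non-significant Mann-Whitney result could then be read as showing that the two devices work equally well. The plan makes no equivalence claim, so this is a risk in reading the result, not an error in a stated conclusion.

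**Working it through.** **1. Which contrast was powered.** The power sentence speaks of pretreatment and post-treatment means. The Statistical analysis section uses the same terms for the within-patient tests and gives the group difference its own sentence and its own test. On the natural reading, the 0.90 belongs to the first contrast only.

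**2. The plan's own figure.** Thirty patients at 0.90 power cannot be reproduced forward without an effect size. It can only be solved backward. Inputs from the plan: total 30, two-sided alpha 0.05, power 0.90, 1:1 allocation. Assumption: 15 analysed per arm.

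- Paired t test: noncentrality = dz × √n, df = n − 1, where dz is the mean change divided by the SD of change.
- Two-sample t test: noncentrality = d × √(n per arm / 2), df = 2 × (n per arm) − 2.

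| Contrast (0.90 power) | Effect needed, in SDs of change | Noncentrality |
|---|---|---|
| Before/after, 30 pooled | 0.612 | 0.612 × √30 = 3.35 |
| Before/after, within one arm of 15 | 0.901 | 0.901 × √15 = 3.49 |
| Between arms, 15 v 15 | 1.226 | 1.226 × √7.5 = 3.36 |

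The between-arm test needs twice the effect of the pooled before/after test (1.226 / 0.612 = 2.0). For 0.80 power it needs 1.060. A between-arm difference of 0.61 SD would have about 0.37 power by t test. These are back-solved illustrations, not the inputs the sponsor used.

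**3. Power of the named test.** Exact two-sided Mann-Whitney, 15 v 15: reject if the smaller U is 64 or less (true size 0.0453). Power was simulated with continuous normal data. SD means the SD of whatever is compared, six-week score or change; the plan does not say which.

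| Difference (SD) | Power |
|---|---|
| 0.5 | 0.24 |
| 0.8 | 0.52 |
| 1.0 | 0.72 |
| 1.11 | 0.80 |
| 1.28 | 0.90 |

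With an assumed 13 per arm, 0.80 and 0.90 power need about 1.20 and 1.39 SD.

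**4. Other scales.** Under normality, the probability that a random patient in the better arm does better than one in the other arm is Φ(d/√2): 0.78 at 1.11 SD and 0.82 at 1.28 SD. If change is compared and the before and after SDs are equal, 1.28 SDs of change equals 1.28 × √(2(1 − r)) raw-score SDs: 1.51, 1.28 and 0.99 at assumed correlations of 0.3, 0.5 and 0.7.

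**5. Non-normal pain scores.** The plan reports the pain score as non-normal, so a tied-score check was run: normal scores with SD 2, rounded and clipped to 0–10, with about 4%, 23% or 40% of the better arm at zero, and a tie-corrected test. At 1.28 SD of the underlying score, power was 0.90, 0.90 and between 0.89 and 0.90. All of these settings are assumed.

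**6. Precision.** The 95% interval for a mean difference at 15 per arm has half-width t(0.975, 28) × √(2/15) = 2.048 × 0.365 = 0.75 SD.

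**The case against.** The strongest reply is that the power sentence may be loose, not wrong. It names no test family, and a difference between before and after means could be shorthand for a change compared between arms. That limits what can be said about the calculation actually run. It does not rescue the text: nothing in the plan says so, and if a between-group or group-by-time test was run, the sentence still needs correcting.

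It is also fair that the Mann-Whitney sentence names no outcome. Taking it as the test of the primary comparison is an inference, though it is the only between-group test in the plan. This should be clarified with the rest.

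Differences of 0.8 to 1.0 SD would be detected more often than not (power 0.52 to 0.72), so the trial is not blind to everything below 1.1 SD; it is conventional power that is reached only there. The correlations, the 13 per arm and the tied-score settings appear nowhere in the plan, and the conclusion does not depend on them.

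Finally, the study is described as already conducted, so its size cannot change. That limits the remedy to description and reporting, both of which can still be put right.

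**Conclusion.** The point holds and should be fixed. As written, the sole sample-size assurance applies to a before/after change and not to the comparison the trial was designed to make. This rests on the plan's own wording and on no assumption about effect size. It is a mismatch between the powered contrast and the objective, not an arithmetic error.

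The size of the shortfall is illustrative. It assumes 15 analysed per arm, two-sided alpha 0.05 and roughly normal data, and it depends on the true difference between orthoses, which the documents do not give. On those terms the group comparison has conventional power only for differences above about 1.1 SD, and an interval spanning about 0.75 SD either side would leave sizeable differences open after a non-significant result.

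**What to change.** 1. State that the 0.90 refers to the before/after contrast and not to the comparison of orthoses. If a between-group or group-by-time calculation was in fact run, correct the sentence and give its effect size and SD.
2. State which outcomes the Mann-Whitney test covers and whether it compares six-week scores or changes. Add the detectable between-group difference at the actual numbers. Illustrative wording, figures to be replaced: *With 15 per arm and two-sided alpha 0.05, the Mann-Whitney comparison of [six-week scores / changes] has about 0.90 power for a difference of about 1.3 SD of that quantity and 0.80 power for about 1.1 SD. These figures assume continuous normal data and are only a guide for the NPRS, which was not normally distributed.*
3. Report between-group differences with 95% confidence intervals: a mean difference for DASH and a Hodges-Lehmann difference for NPRS. A t-based interval for DASH can occasionally disagree with the Mann-Whitney p-value, so say which one is the main result.
4. State that a non-significant result is not evidence of equal efficacy.

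The cost is some rewording and two intervals from data already collected. The stated assurance becomes less favourable.

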# Study sample

Patients were randomly assigned in a 1:1 ratio to either the MCP-blocking group or the RME group, using a simple random sampling method. Patients were numbered according to their admission to the clinic. Randomization was performed using a random number table system. Starting with the MCP-blocking group, each group was assigned a number in turn. Patients in the MCP group received an MCP-blocking orthosis, and patients in the RME group received an RME orthosis for six weeks. All patients received patient education, activity modification, and flexor tendon gliding exercises as part of the rehabilitation program.

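### Stage is known before allocation, but neither the allocation nor the between-group test uses it: with about 30 patients this costs precision and leaves a chance severity imbalance uncorrected

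*Combined protocol and SAP*

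**What the plan says.** Study design sets the eligible range: "The inclusion criteria were patients diagnosed with Stage 1-3 trigger finger, A1 pulley triggering and aged between 18 and 60 years". Stage therefore has to be established before a patient is allocated. The same section gives the size: "A total sample of 30 participants was required to achieve a power of 0.90". The calculation behind it was made "to test the difference between pretreatment and post-treatment means with a two-tailed test", so it addresses change over time and not the contrast between orthoses.

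Study sample describes the allocation: "Patients were randomly assigned in a 1:1 ratio to either the MCP-blocking group or the RME group, using a simple random sampling method". It adds: "Randomization was performed using a random number table system". No blocking, stratification or minimisation is mentioned. The section also says that numbers went to the groups alternately, MCP-blocking first.

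The list of pre-treatment data under Measurements does not include stage. Pain (NPRS) and function (DASH) are measured before treatment and at six weeks. On the comparison of the arms, Statistical analysis says only: "The Mann-Whitney U test was used to analyse the difference between two groups". It names no covariate or stratum.

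**The concern.** If stage predicts six-week pain or disability, it matters in two ways in a trial of this size. First, variation between stages stays in the error term of an unadjusted comparison, so power is lost even when the arms happen to balance. Second, when one arm receives clearly more stage 3 patients, the observed difference mixes severity with the orthosis, and nothing in the planned analysis separates them. Because stage is not among the listed baseline data, a reader might not even see the imbalance.

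**Working it through.** **The plan's own figure.** The total of 30 rests on "an alpha of 0.05", two-sided, and power 0.90, but the documents give no effect size or SD. It cannot be reproduced, only back-solved from the noncentral t distribution (noncentrality d√n for paired data, d√(n/2) between arms):
- pre-post, 30 patients pooled: standardised change 0.61
- pre-post, 15 patients in one arm: 0.90
- between arms, 15 per arm: 1.23

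The between-arm comparison thus reaches 90% power only for a very large effect and has little precision to spare.

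**Inputs for the imbalance check.** From the documents: total 30, 1:1 ratio (15 per arm), stages 1-3, unadjusted Mann-Whitney test. Assumed: 10 of 30 patients in stage 3; stage 3 worse at six weeks by 10-20 DASH points, with a within-stage SD of 15-20. The stage gap then runs from 10/20 = 0.5 SD to 20/15 = 1.33 SD.

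**Step 1: how often stage 3 splits unevenly.**
- Coin-toss allocation, Binomial(10, 0.5): 7:3 or worse = 2(120+45+10+1)/1024 = 0.344; 8:2 or worse = 2(45+10+1)/1024 = 0.109.
- Arms fixed at 15:15, hypergeometric (10 stage 3 among 30, 15 drawn): 0.245 and 0.050.

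The result depends on the assumed stage share. At shares of 20%, 33% and 50%, with 15 per arm, a given stage differs by 3 or more patients in 25%, 33% and 36% of trials, and by 5 or more in 4%, 8% and 10%.

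**Step 2: what an uneven split does to the arm difference.** Shift = (difference in stage 3 counts / 15) × gap.
- 7:3: 4/15 × 10-20 = 2.7-5.3 DASH points
- 8:2: 6/15 × 10-20 = 4-8 DASH points

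For scale, SD × √(2/15) is 5.5 at SD 15 and 7.3 at SD 20.

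**Step 3: false-positive rate of the planned test.** This was simulated with normal outcomes, 15 per arm, stage gaps of 0.5-1.33 within-stage SD and no orthosis effect:
- over all random allocations: 4.2-4.6%
- given a 7:3 split: about 5-8%
- given an 8:2 split: about 7-18%

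The excess in unbalanced trials is offset by a lower rate in balanced ones, so the overall rate holds.

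**Step 4: precision.** With one third of patients in stage 3, the unadjusted variance is larger than the within-stage variance by p(1−p) × gap² = (1/3)(2/3) × gap². This is 0.056 at 0.5 SD and 0.39 at 1.33 SD, or about 6-39%. Ignoring the one degree of freedom, 30 unadjusted patients are worth about 30/1.06 = 28 to 30/1.39 = 22 adjusted ones.

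For an orthosis effect of 1 SD, power rises from about 56-68% with the Mann-Whitney test to 74% with a stage term in a linear model. Nothing is lost against the planned test if stage has no effect. Part of this gain, and at a gap of 0.5 SD most of it, comes from replacing a rank test by a linear model on normal data. The part due to stage grows with the gap.

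**Step 5: does adjustment repair the unbalanced trials?** In a separate simulation with stage gaps of 0.5 and 1.0 SD, a stage-adjusted linear model kept the false-positive rate at 4.7-5.2% when a stage differed by 3 or more patients, and at about 4-6.5% when it differed by 5 or more.

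**The case against.** The strongest reply is that unstratified random allocation is a valid design and that the test already allows for chance imbalance. This stands. A reader might infer that the trial's error rate is inflated or that the design is biased. The overall rate of 4.2-4.6% rules that out under genuine randomisation. The higher rates apply only after an unlucky split.

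A reader might also infer that a serious imbalance is likely. For one named stage it is a minority event. With three equally common stages, at least one differs by 3 or more patients in 59% of trials, but that is a weaker statement about a moderate difference.

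A quick noncentral t calculation with the SD held fixed gives conditional rates of 6-16% (7:3) and 8-29% (8:2). These are too high. The shortcut adds the stage shift to the difference but leaves stage variation out of the standard error, and it replaces the named rank test by a t test.

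Nor do the documents support the claim that the 1:1 ratio would fail. Coin-tossing would give exactly 15:15 in only 14% of trials, but the alternating wording in Study sample may mean that arm sizes were fixed. How that wording fits with random allocation is a separate point to reconcile. It does not settle this one, since alternation ignores stage as well.

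Finally, stage grades triggering, while the outcomes are patient-reported, and no passage links the two. Baseline NPRS and DASH capture part of severity. Both remarks are fair, but the plan describes no baseline adjustment between arms either.

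**Conclusion.** The point holds as one of precision and interpretability. Stage is available, allocation ignores it, the between-group test does not adjust for it, and it is not listed for reporting. With 10 of 30 patients in stage 3 and 15 per arm, about one trial in four splits 7:3 or worse and about one in twenty 8:2 or worse (34% and 11% under coin-tossing). The planned test's conditional false-positive rate is then about 5-8% at 7:3 and 7-18% at 8:2. The upper ends need a stage effect of 1.33 SD. The stage mix, the stage effect and normal outcomes are all assumptions. The plan itself describes NPRS as not normally distributed, so the power figures fit DASH better. If stage has little bearing on the outcomes, the loss is small. The case for acting is that the remedy costs almost nothing.

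**What to change.** - **Measurements:** add stage at entry to the baseline data and report it by arm. Study design places recruitment between June 2021 and March 2022, so stage may have to come from eligibility records.
- **Statistical analysis:** compare six-week NPRS and DASH between groups with a stage term (stages 1-2 versus stage 3). If the rank test is kept, use the stage-stratified Wilcoxon (van Elteren) test. The power figures above are for the linear model; none was computed for van Elteren. The two-level cut is a practical choice for a small sample, not one that the documents supply.
- **Study sample, only if allocation can still be changed:** use permuted blocks of varying size (2 and 4) within the two stage strata. This limits the difference in each stratum to at most 2 patients.

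The analysis change costs one degree of freedom and no patients or visits. Stratified allocation needs two lists instead of one, and the last block in each stratum may stay incomplete, so arm sizes can differ by a few patients.

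### The trial aims to compare two orthoses, but it is sized on, and also tests, pre/post change, which cannot isolate either device; the between-arm difference should carry the conclusion

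*Combined protocol and SAP*

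**What the plan says.** Study design gives the purpose as to "compare the efficacy of metacarpophalangeal (MCP)-blocking orthosis with relative motion extension (RME) orthosis in patients with trigger finger". The same section bases the sample size on a different contrast. The calculation was done "to test the difference between pretreatment and post-treatment means with a two-tailed test", with "an alpha of 0.05", and concludes: "A total sample of 30 participants was required to achieve a power of 0.90". No effect size, standard deviation, pre/post correlation or dropout rate is given. The section does not say whether the pre/post test pools the arms or is run within each.

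Study sample describes two active arms: "Patients were randomly assigned in a 1:1 ratio to either the MCP-blocking group or the RME group". Each arm wears its orthosis for six weeks, and the rehabilitation content is common to both: "All patients received patient education, activity modification, and flexor tendon gliding exercises as part of the rehabilitation program". There is no arm without an orthosis. Measurements schedules the primary outcomes, pain (NPRS) and function (DASH), before treatment and at six weeks only.

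Statistical analysis lists the pre/post tests first: a Student t test for normally distributed data, while a "two-tailed Wilcoxon signed rank test was used for non-normally distributed data to compare pretreatment and post-treatment results". A Mann-Whitney U test between groups follows. The section does not say whether that test compares six-week scores or changes, and it does not rank the two kinds of test.

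**The concern.** The contrast that was powered is not the contrast that answers the aim. A pre/post change in either arm, or in all patients together, is the sum of at least four things: the orthosis, the shared rehabilitation programme, the natural course over six weeks, and regression to the mean in patients who came to clinic with symptoms. With no arm lacking an orthosis and only two assessments, no analysis of these data can separate them. A larger sample would not help, because it would only make the same mixture more precise.

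What the randomisation does isolate is one orthosis against the other, each on top of the same programme. That comparison has no power statement and no declared priority. A plausible outcome is therefore a significant pre/post change beside a non-significant between-arm test. Without a stated rule, that pattern could be read as showing that both devices work, which no comparison in this trial can support.

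**Working it through.** **Inputs from the documents.** Total N = 30, power 0.90, two-sided alpha 0.05, pre/post contrast (Study design); 1:1 allocation (Study sample), hence 15 per arm.

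**Assumptions.** The documents do not supply the rest. I use a paired t test, with changes expressed in units of the SD of change, and independent arms. NPRS is assigned to the Wilcoxon test, so for that outcome the t-based figures are only an approximation.

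**Step 1: the plan's own figure.** N = 30 cannot be reproduced, because no effect size is stated; it can only be back-solved. Power = P(T > t[0.975, n − 1]), where T is noncentral t with n − 1 degrees of freedom and noncentrality dz × √n. Setting power to 0.90:
- all 30 pooled: dz = 0.612 (noncentrality 0.612 × √30 = 3.35);
- one arm of 15: dz = 0.901 (noncentrality 0.901 × √15 = 3.49).

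The implied change is thus about 0.61 or about 0.90, depending on a choice the plan does not state.

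**Step 2: what the pre/post test does when the orthoses contribute nothing.** Suppose the shared programme, natural course and regression to the mean alone produce the change. The same formula gives the first two columns of results. The last column is the square of the one-arm probability.

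| Shared change (SD of change) | Significant, pooled 30 | Significant, one arm of 15 | Significant in both arms, one outcome |
|---|---|---|---|
| 0.5 | 75% | 44% | 0.44² = 19% |
| 0.61 | 90% | about 60% | 0.60² = 36% |
| 0.8 | 99% | 82% | 0.82² = 67% |
| 0.90 | nearly 100% | 90% | 0.90² = 81% |

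A simulation of 20,000 trials with 15 per arm and a common normal change agrees. At 0.61 it gave 0.898 pooled, 0.597 in one arm and 0.36 in both; at 0.90 it gave 0.81 in both.

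**Step 3: what the between-arm test does in the same situation.** In the same simulation, with no difference between devices, the two-sample t test was significant in 4.8% to 5.0% of trials. The Mann-Whitney U test on changes (4,000 trials) was significant in 4.2% to 4.9%. This held at every shared change tried, from 0 to 1.2 SD. The shared programme leaves the randomised contrast unbiased.

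**Step 4: precision of the between-arm test.** Power uses noncentral t with 28 degrees of freedom and noncentrality d × √(15/2). The values of d are assumed.
- d = 0.5: noncentrality 1.37, power 26%; 90% power would need 86 per arm.
- d = 0.8: noncentrality 2.19, power 56%; 90% power would need 34 per arm.
- 15 per arm reaches 90% power only at d of about 1.23.

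The 0.90 in Study design therefore does not carry over to the comparison named in the aim.

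**The case against.** The strongest reply is that this is a head-to-head trial and says so. Identical co-treatment in both arms is sound practice for such a design, a between-group test is planned, and a rehabilitation-only arm is needed only if someone claims that an orthosis beats rehabilitation alone. All of that stands. The common programme is not a defect.

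Three stronger readings are tempting and should not be drawn.

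- A reader might infer that the plan will credit a significant pre/post p-value to the device. No section says so. The documents contain no conclusion and no rule of interpretation, so the risk is a misreading that the plan leaves open.
- A reader might infer that the trial will probably show significant improvement with each orthosis even if neither adds anything. At a shared change of 0.61 SD, both arms are significant only about 36% of the time for one outcome, and requiring both pain and function cannot raise that. It becomes likely only at larger shared changes, and the documents give no figure for the shared change.
- A reader might take 0.61 as the plan's own effect size. It is a back-solved value that holds only if the arms are pooled.

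What the reply does not meet is the mismatch in Study design. The only powered contrast is the one that cannot answer the aim, and Statistical analysis gives it at least equal standing with the one that can.

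**Conclusion.** The point holds as a should-fix. The sample size and the first-listed tests concern pre/post change, whereas the aim concerns the difference between two orthoses, and nothing says which result decides. This mismatch can be read directly from the text and needs no assumption.

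The size of the risk does rest on assumptions: a paired t test, 15 per arm, and a shared change that the documents do not give. Over shared changes of 0.5 to 0.90 SD with no device effect, a pooled pre/post test would be significant from 75% to nearly 100% of the time, and both arms together from 19% to 81%. The severity stops short of must-fix because the randomised estimate is not biased by this issue and the harm depends on a conclusion that the documents do not draw.

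**What to change.** In Statistical analysis:
- Report pre/post change in each arm descriptively, as a mean or median change with a confidence interval and no significance test.
- Name the between-arm difference in NPRS and DASH at six weeks as the primary analysis, with a confidence interval. State whether it is a difference in change or a baseline-adjusted difference.
- Make that difference the sole basis for efficacy conclusions, read as one orthosis versus the other, each added to the same programme.
- State that the design cannot show either orthosis to be better than the programme alone, and that a non-significant between-arm result does not show that both work.

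In Study design, state that the 0.90 power applies to the pre/post difference and not to the between-arm comparison.

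No new arm, patients or measurements are needed. The cost is a more modest claim and a primary comparison that is openly imprecise: with 15 per arm, about 26% power at an assumed d of 0.5 and 56% at an assumed d of 0.8.
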